Abbreviations: AE, adverse event; BPI-SF, Brief Pain Inventory-Short Form; CGI-I, Clinical Global Impression-Improvement; PGI-C, Patient-Global Impression of Change; eICF, electronic informed consent form; EQ5D-5L-European QoL; ST, Spectrum Therapeutics.

¹. The subject-verified visits will only include numeric rating scale pain items from the BPI.

². EQ5D-5L- QoL (5 category questionnaires to be completed by the subject)

³. AEs recorded by the subject at subject-verified follow-ups will be assessed by the physician at physician verified follow-up.

ABBREVIATIONS AND DEFINITIONS OF TERMS

Abbreviation/Term	Definition
AE	Adverse event
BMI	Body mass index
BPI-SF	Brief Pain Inventory-Short Form
CBD	Cannabidiol
CGI-I	Clinician Global Impression-Improvement
eCRF	Electronic case report form
ECS	Endocannabinoid system
eICF	Electronic informed consent form
EQ5D-5L	Euro Quality of Life (QoL)
GCP	Good Clinical Practice
GPVD	Global Pharmacovigilance Department
IASP	International Association for the Study of Pain
ICF	Informed consent form
ICH	International Council for Harmonization
IME	Important Medical Event List
MME	Milligram morphine equivalents
MSL	Medical science liaison
NRS	Numeric rating scale
PGI-C	Patient Global Impression of Change
SAE	Serious adverse event
SD	Standard deviation
ST	Spectrum Therapeutics

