3. STUDY DESIGN

3.1 Description of the Study

The present study is a prospective, observational registry designed to generate real-world data on the physician-recommended use of ST products to manage chronic pain in countries where these products are commercially available. The study will enroll up to 1500 subjects from 50-150 sites in geographic regions of ST product distribution over a two-year period. Physicians will recruit subjects during routine care visits and assess whether subjects with chronic pain are candidates for medical cannabis treatment. Once enrolled, subjects will be followed for 1 year to collect data on demographics, chronic pain classification, cannabis experience, treatment goals, concomitant medication(s), ST treatment regimen, clinical assessment, subject-reported outcomes, and safety.

The study includes five physician-verified visits (baseline, 2, 4, 8, and 12 months), and four at-home subject-verified follow-ups (months 1, 3, 6, 10). Physician verified follow ups can be conducted in person or via telemedicine. Additionally, should there be a need, according to the physician's judgement, there may be other unscheduled visits, either in-clinic, or via telemedicine. All data will be collected using *REDCap Cloud* via online eCRFs. The study time-points were selected based on the typical timeframe of titration in routine care, and adverse event (AE) emergence for the use of cannabis products in new subjects; a majority of titration occurs within the first month of taking a new cannabis product²⁹. Visits were also spaced out so that subject retention may be maximized, and treatment adjusted in a timely manner. Later time-points are designed to capture longer-term treatment-related outcomes while screening for AE emergence and medication use changes in the long term.

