7. OUTCOME ASSESSMENTS

7.1 Study Endpoints

Primary endpoints

- Physician selection of Spectrum Therapeutics (ST) medical cannabis treatment regimen and changes over time in:
 - (1) average daily dose of THC and CBD (in mg);
 - (2) route of administration (inhaled or ingested).

Secondary endpoints

- Subject selection of ST treatment regimen and changes over time in:
 - (1) average daily dose of THC and CBD (in mg);
 - (2) route of administration (inhaled or ingested).
- Change in BPI-SF responses from baseline.
- Change in EQ5D-5L responses from baseline.
- PGI-C for the target treatment goal.
- CGI-I for the target treatment goal.
- In subjects taking an opioid, changes in opioid use over time (calculated as milligram morphine equivalents [MME]/day).
- Among subjects taking other medication, total daily dose change over time.

Safety endpoint

- Incidence of AEs stratified by product and formulation.

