7.2.2 BPI-SF

The BPI-SF is a 9-item self-report questionnaire that is quickly and easily administered to subjects with chronic pain. The questionnaire includes 6 pain items that assess the spatial and temporal characteristics of pain (e.g., location, 24-hour worst pain, 24-hour average pain, pain right now); 2 items that ask about current treatments assumed for chronic pain and pain relief; and 1 pain interference item (with parts A–G) where respondents rate the level of interference of pain with general activity, mood, walking ability, normal work, social relations, sleep, and enjoyment of life over the past 24 hours²⁴.

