Yellow (examples include Tweed CBD Softgels)	 inhalations  	 mL  	 sprays  	 capsules  	 capsules  
Spectrum Clear (or White)		 mL  			

You indicated that your patient has been recommended an inhaled format. Please identify their most common method of administration.

(inhal_admin)

[Branching logic exists]

- Smoked
- Dried flower vaporizer (e.g. Stroz and Bickel, PAX)
- Extract vaporizer (e.g. vape pen cartridge)

Do you or your patient know the temperature set point of the vaporizer (in °C)

(inhal_vape_Y/N)

[Branching logic exists]

- Yes
- No

If known, please provide the temperature set point of your patient's vaporizer (in °C) _____

(inhal_vape_temp)

(125 / 300)

[Branching logic exists]

Calculated, approximated total daily dose of THC and CBD (in mgs)

	THC	CBD
Inhaled	
(inhal_THC)
  
View Equation
	
(inhal_CBD)
  
View Equation

Ingested	
(ingest_THC)
  
View Equation
	
(ingest_CBD)
  
View Equation

Patient reported outcomes

BPI

Throughout our lives, most of us have had pain from time to time (such as minor headaches, sprains, and toothaches). Have you had pain other than these everyday kinds of pain today?

- Yes
- No

Please select the number (0= no pain, 10= pain as bad as you can imagine) that best describes your pain at its worst in the last 24 hours.

- 0
- 1
- 2
- 3
- 4
- 5
- 6
- 7
- 8
- 9
- 10

Please select the number (0= no pain, 10= pain as bad as you can imagine) that best describes your pain at its least in the last 24 hours.

- 0
- 1
- 2
- 3
- 4
- 5
- 6
- 7
- 8
- 9
- 10

Please select the number (0= no pain, 10= pain as bad as you can imagine) that best describes your pain on the average.

- 0
- 1
- 2
- 3
- 4
- 5
- 6
- 7
- 8
- 9
- 10

Please select the number (0= no pain, 10= pain as bad as you can imagine) that best describes how much pain you have right now.

- 0
- 1
- 2
- 3
- 4
- 5
- 6
- 7
- 8
- 9
- 10

Please select the number (0= does not interfere, 10= completely interferes) that best describes how, during the past 24 hours, pain has interfered with your: **General Activity**

- 0
- 1
- 2
- 3
- 4
- 5
- 6
- 7
- 8
- 9
- 10

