Please select the number (0= no pain, 10= pain as bad as you can imagine) that best describes your pain at its least in the last 24 hours.

- 0
- 1
- 2
- 3
- 4
- 5
- 6
- 7
- 8
- 9
- 10

Please select the number (0= no pain, 10= pain as bad as you can imagine) that best describes your pain on the average.

- 0
- 1
- 2
- 3
- 4
- 5
- 6
- 7
- 8
- 9
- 10

Please select the number (0= no pain, 10= pain as bad as you can imagine) that best describes how much pain you have right now.

- 0
- 1
- 2
- 3
- 4
- 5
- 6
- 7
- 8
- 9
- 10

Please select the number (0= does not interfere, 10= completely interferes) that best describes how, during the past 24 hours, pain has interfered with your: **General Activity**

- 0
- 1
- 2
- 3
- 4
- 5
- 6
- 7
- 8
- 9
- 10

Please select the number (0= does not interfere, 10= completely interferes) that best describes how, during the past 24 hours, pain has interfered with your: **Mood**

- 0
- 1
- 2
- 3
- 4
- 5
- 6
- 7
- 8
- 9
- 10

Please select the number (0= does not interfere, 10= completely interferes) that best describes how, during the past 24 hours, pain has interfered with your: **General Activity**

- 0
- 1
- 2
- 3
- 4
- 5
- 6
- 7
- 8
- 9
- 10

Please select the number (0= does not interfere, 10= completely interferes) that best describes how, during the past 24 hours, pain has interfered with your: **Mood**

- 0
- 1
- 2
- 3
- 4
- 5
- 6
- 7
- 8
- 9
- 10

Please select the number (0= does not interfere, 10= completely interferes) that best describes how, during the past 24 hours, pain has interfered with your: **Walking ability**

- 0
- 1
- 2
- 3
- 4
- 5
- 6
- 7
- 8
- 9
- 10

Please select the number (0= does not interfere, 10= completely interferes) that best describes how, during the past 24 hours, pain has interfered with your: **Normal work (includes both work outside the home and housework)**

- 0
- 1
- 2
- 3
- 4
- 5
- 6
- 7
- 8
- 9
- 10

Please select the number (0= does not interfere, 10= completely interferes) that best describes how during the past 24 hours, pain has interfered with your: **Relations with other people**

- 0
- 1
- 2
- 3
- 4
- 5
- 6
- 7
- 8
- 9
- 10

Please select the number (0= does not interfere, 10= completely interferes) that best describes how during the past 24 hours, pain has interfered with your: **Sleep**

- 0
- 1
- 2
- 3
- 4
- 5
- 6
- 7
- 8
- 9
- 10

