[Branching logic exists]

If known, please provide the temperature set point of your patient's vaporizer (in °C) _____

(inhal_vape_temp)
(125 / 300)
[Branching logic exists]

Calculated, approximated total daily dose of THC and CBD (in mgs)		
	THC	CBD
Inhaled	(inhal_THC)  View Equation	(inhal_CBD)  View Equation
Ingested	(ingest_THC)  View Equation	(ingest_CBD)  View Equation

Side Effects

Does your daily dose include any side effects (e.g. nausea, dry mouth, drowsiness, euphoria, etc.)?

- Yes
- No

You indicated that you experience side effects from your daily dose. Please indicate which side effects you experience (check all that apply)

- Nausea
- Dry Mouth
- Dizziness
- Somnolence (i.e. sleepiness/drowsiness)
- Euphoria
- Other

Please describe the 'other' side effects that you experienced

Subject Adverse Event Reporting

AE diary

Since you have been taking Spectrum Therapeutics medical cannabis products, have you experienced any side effects? Please include any side effects you have experienced, regardless of whether you believe they are related to medical cannabis.

- Yes
- No

Please describe in as much detail the adverse event (side effect) that you experienced.

Adverse events, symptoms, start date/end date, event(s) chronology, treatments, outcome.

PGI-C

Global Impression of Change

Since the start of Spectrum Therapeutics treatment, my overall symptom status is:

(best describe how your symptom is now, compared with how it was before you began taking medical cannabis)

- Very Much Improved
- Much Improved
- Minimally Improved
- No Change
- Minimally Worse
- Much Worse
- Very Much Worse

Patient reported outcomes

BPI

Throughout our lives, most of us have had pain from time to time (such as minor headaches, sprains, and toothaches). Have you had pain other than these everyday kinds of pain today?

- Yes
- No

Please select the number (0= no pain, 10= pain as bad as you can imagine) that best describes your pain at its worst in the last 24 hours.

- 0
- 1
- 2
- 3
- 4
- 5
- 6
- 7
- 8
- 9
- 10

Please select the number (0= no pain, 10= pain as bad as you can imagine) that best describes your pain at its least in the last 24 hours.

- 0
- 1
- 2
- 3
- 4
- 5
- 6
- 7
- 8
- 9
- 10

Please select the number (0= no pain, 10= pain as bad as you can imagine) that best describes your pain on the average.

- 0
- 1
- 2
- 3
- 4
- 5
- 6
- 7
- 8
- 9

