- 10

Please select the number (0= no pain, 10= pain as bad as you can imagine) that best describes how much pain you have right now.

- 0
- 1
- 2
- 3
- 4
- 5
- 6
- 7
- 8
- 9

Please select the number (0= does not interfere, 10= completely interferes) that best describes how, during the past 24 hours, pain has interfered with your: **General Activity**

- 0
- 1
- 2
- 3
- 4
- 5
- 6
- 7
- 8
- 9
- 10

Please select the number (0= does not interfere, 10= completely interferes) that best describes how, during the past 24 hours, pain has interfered with your: **Mood**

- 0
- 1
- 2
- 3
- 4
- 5
- 6
- 7
- 8
- 9
- 10

Please select the number (0= does not interfere, 10= completely interferes) that best describes how, during the past 24 hours, pain has interfered with your: **Walking ability**

- 0
- 1
- 2
- 3
- 4
- 5
- 6
- 7
- 8
- 9
- 10

Please select the number (0= does not interfere, 10= completely interferes) that best describes how, during the past 24 hours, pain has interfered with your: **Normal work (includes both work outside the home and housework)**

- 0
- 1
- 2
- 3
- 4
- 5
- 6
- 7
- 8
- 9
- 10

Please select the number (0= does not interfere, 10= completely interferes) that best describes how during the past 24 hours, pain has interfered with your: **Relations with other people**

- 0
- 1
- 2
- 3
- 4
- 5
- 6
- 7
- 8
- 9
- 10

Please select the number (0= does not interfere, 10= completely interferes) that best describes how during the past 24 hours, pain has interfered with your: **Sleep**

- 0
- 1
- 2
- 3
- 4
- 5
- 6
- 7
- 8
- 9
- 10

Please select the number (0= does not interfere, 10= completely interferes) that best describes how during the past 24 hours, pain has interfered with your: **Enjoyment of life**

- 0
- 1
- 2
- 3
- 4
- 5
- 6
- 7
- 8
- 9
- 10

EQ5D

Mobility

- I have no problems in walking about
- I have slight problems in walking about
- I have moderate problems in walking about
- I have severe problems in walking about
- I am unable to walk

Self-Care

- I have no problems washing or dressing myself
- I have slight problems washing or dressing myself
- I have moderate problems washing or dressing myself
- I have severe problems washing or dressing myself
- I am unable to wash or dress myself

Usual Activities

- I have no problems doing my usual activities
- I have slight problems doing my usual activities
- I have moderate problems doing my usual activities
- I have severe problems doing my usual activities

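### As printed, the home form's pain-right-now item stops at 9 although its anchor and both physician forms run to 10; check the live field and restore option 10

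*Protocol*

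**What the plan says.** Section 7.1 of the protocol lists as a secondary endpoint "Change in BPI-SF responses from baseline", and Section 9.1 names change in the individual BPI-SF items among the outcome analyses. Section 3.1 sets "four at-home subject-verified follow-ups (months 1, 3, 6, 10". Footnote 1 to Table 1 confirms that the pain ratings belong to those contacts: "The subject-verified visits will only include numeric rating scale pain items from the BPI".

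The three forms print the current-pain item as follows.

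- Appendix 1 (baseline): "that best describes how much pain you have right now", options 0 to 10.
- Appendix 2 (months 2, 4, 8 and 12): same wording, options 0 to 10.
- Appendix 3 (home): "0= no pain, 10= pain as bad as you can imagine) that best describes how much pain you have right now", options 0 to 9, with the General Activity question directly after the 9.

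Section 7.2.2 describes the interference part of the instrument as "1 pain interference item (with parts A–G", that is, seven ratings. In Appendix 2 the rating of "how, during the past 24 hours, pain has interfered with your: General Activity" appears twice and so does the Mood rating, which makes nine.

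**The concern.** The Appendix 3 item contradicts its own anchor, the other BPI items on the same form and the same item on both physician forms. If the live form follows the print, baseline and the physician visits use an 11-point scale and the home contacts a 10-point scale.

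The distortion would have one direction: it can only lower recorded pain. It would arise only after baseline and only in subjects reporting the worst pain. The registry has no comparison group in which the same artefact would cancel. It would also put a form effect between home and clinic visits into any longitudinal model of this item. If subjects skip the item because their answer is not offered, missingness depends on the unrecorded value itself. The missing-at-random assumption in Section 9.3, which is stated for dropout, does not cover that case, and the same section says that descriptive summaries are not imputed.

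**Working it through.** **Step 1: is the 10 really absent?** Going through the BPI block of Appendix 3 item by item, worst pain, least pain and "that best describes your pain on the average" each list 0 to 10, and so do all seven interference items. The current-pain item alone ends at 9. The forms compare as follows.

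| Current-pain item | Used at | Anchor | Printed options |
|---|---|---|---|
| Appendix 1 | baseline | 10 | 0 to 10 |
| Appendix 2 | months 2, 4, 8, 12 | 10 | 0 to 10 |
| Appendix 3 | months 1, 3, 6, 10 | 10 | 0 to 9 |

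**Step 2: effect on one subject, if built as printed.**

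- True 10 at baseline and 10 at home, entered as 9: 9 - 10 = -1, where the true change is 0.
- Same subject, item skipped: change is missing.
- True 9 at baseline and 10 at home, entered as 9: 9 - 9 = 0, where the true change is +1.

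**Step 3: effect on the mean when 10s are entered as 9.** The protocol states no figure for this, so there is none to reproduce. Assumption: scores are a normal variable rounded to 0 to 10, with no true change in the group. Each subject at 10 loses one point, so the false mean change equals -P(10), with P(10) = 1 - Φ((9.5 - mean)/SD).

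| Mean | SD | P(10) | Of 1500 | False mean change |
|---|---|---|---|---|
| 5 | 2 | 1 - Φ(2.25) = 0.012 | 18 | -0.01 |
| 5 | 2.5 | 1 - Φ(1.80) = 0.036 | 54 | -0.04 |
| 6 | 2 | 1 - Φ(1.75) = 0.040 | 60 | -0.04 |
| 6 | 2.5 | 1 - Φ(1.40) = 0.081 | 121 | -0.08 |
| 7 | 2 | 1 - Φ(1.25) = 0.106 | 158 | -0.11 |
| 7 | 2.5 | 1 - Φ(1.00) = 0.159 | 238 | -0.16 |

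For scale, at the planned maximum of 1500 subjects and an assumed SD of change of 2, the standard error of a mean change is 2/√1500 = 0.05.

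**Step 4: effect when 10s are left blank.** A subject with a blank follow-up has no change score, so the paired mean is taken over those who answered. I simulated baseline and home scores from the extreme case of Step 3 (mean 7, SD 2.5, no true group change), dropped home scores of 10, and averaged the remaining changes.

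| Within-subject correlation | Paired false change |
|---|---|
| 1 | 0.00 |
| 0.9 | -0.07 |
| 0.7 | -0.18 |
| 0.5 | -0.29 |
| 0 | -0.59 |

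**Step 5: Appendix 2.** Printed interference ratings: General Activity, Mood, General Activity, Mood, walking, work, relations, sleep, enjoyment, nine in all. Appendix 1 and Section 7.2.2 have seven. Two items would then have two answers at each physician follow-up.

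**The case against.** **The print may not be the instrument.** Data are captured in REDCap Cloud, and Appendix 3 is visibly a loose copy: the subject's own form asks about a patient's vaporizer and heads its table as the physician's recommended regimen. The text at hand was also read from PDF by a program, so one short line could have been lost, and the repeated block in Appendix 2 could come from overlapping page captures. This stands. A reader might infer that subjects in maximal pain are in fact being recorded as improved or missing. The document does not support that; it shows only what would happen if the live form matches the page.

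**The reach is narrow.** Worst, least and average pain run 0 to 10 on the same home form, so pain change at month 1 can still be estimated. Months 2, 4, 8 and 12 are clean for this item, and the primary endpoint (dose and route) is untouched. Nothing in the protocol gives current pain special weight among the four intensity items. This stands too.

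**Two larger effects are tempting but not supported.** One could compare the mean of those who answer with the mean of everyone and report up to -0.59 points as false improvement when 10s are skipped. That is a shift between visit means over different subjects. As a change from baseline it appears only if baseline and home scores are unrelated. Likewise, one could average the nine printed interference ratings and show a distorted score, but the protocol defines no such composite and analyses items singly.

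None of this removes the contradiction on the page between the item's anchor and its options.

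**Conclusion.** The inconsistency holds as a fault in the printed form, and its consequence is conditional on the live build. At subject level the error is at most one point per home contact, always towards less pain. At group level it is about -0.01 to -0.16 points when 10s are entered as 9. The upper end requires about 16% of subjects to score exactly 10, and the whole range rests on an assumed distribution. When 10s are skipped, the effect on paired change runs from zero upwards in size as within-subject correlation falls, and the protocol gives no correlation.

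The point is modest: ceiling scores, one of four intensity items, four of eight follow-ups, a secondary endpoint. It still merits correction, because once data are collected a home 9 cannot be told apart from a truncated 10. The repeated interference items in Appendix 2 are a minor copy fault with no analytic effect that the protocol itself defines.

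**What to change.** 1. Check the source page of Appendix 3 and the option list of the live REDCap Cloud field. If the live field offers 10, correct the appendix only.
2. Add option 10 to the current-pain item in Appendix 3, and in the live form if it is missing there.
3. If home data were already collected on 0 to 9, either base change from baseline for this item on months 2, 4, 8 and 12, or treat a home value of 9 as censored at 9 or above.
4. Delete the second General Activity and Mood items from Appendix 2, so that each item has one answer per visit as in Section 7.2.2, and confirm that the live form shows them once.

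Before data collection the cost is one response option, two deletions and a field check. Afterwards it is a sentence of analysis wording and, if the first choice in step 3 is taken, the loss of four home time points for one item.

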Appendix 4 ST Discontinuation Assessment

ST Discontinuation

Date of Spectrum Therapeutics treatment discontinuation

(YYYY-MM-DD)

Why did your patient discontinue Spectrum Therapeutics treatment?

- Adverse Event
- Didn't like/uncomfortable (not associated with an AE) with cannabis
- Lack of patient overall treatment satisfaction
- Lack of physician overall treatment satisfaction
- Patient switched to prescription cannabinoids (nabilone, dronabinol, nabiximols)
- Patient is obtaining cannabis for medical purposes from a different licensed producer
- Patient is obtaining cannabis for medical purposes from a non-licensed source
- Symptom(s) no longer present
- Unable to afford Spectrum Therapeutics cannabis/no coverage
- No longer wanted to participate in the registry
- Difficulties accessing medical cannabis (regulatory or logistics barriers)
- Patient is deceased
- Other

Is your patient still taking cannabis for medical purposes?

- Yes
- No

Please describe "other" or include further comments regarding treatment discontinuation

Is your patient obtaining cannabis for medical purposes from an alternative source?

- Yes
- No

Given the response provided for "Why your patient discontinued Spectrum Therapeutics treatment?", they are still eligible for participation in the registry. Does your patient wish to continue to participate in the registry?

- Yes
 No

Please indicate which medical cannabis company

Please indicate why (select all that apply)

- More product variety within categories offered by Spectrum Therapeutics (e.g. more strains of dried flower)
- More product categories not offered by Spectrum Therapeutics (e.g. edible formats)
- Pricing
- Insurance coverage
- Product quality
- Product availability
- Other

Please describe other

Based on the response provided for "Why your patient discontinued Spectrum Therapeutics treatment?", they no longer meet the requirements for participation in the registry. Please confirm their withdrawal from the study using the 'Exit Assessment' form.

Based on the response provided for "Does your patient wish to continue to participate in the registry?", we kindly request that you confirm their withdrawal from the study using the 'Exit Assessment' form.

Thank you for your on-going participation in the study. Please continue to follow the protocol and complete scheduled follow-ups. With respect to the tables requesting information on the "Regimen of Spectrum Therapeutics Products", simply reply "No" to the question "Is your patient still taking Spectrum Therapeutics products" and submit.

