Do you or your patient know the temperature set point of the vaporizer (in °C)
(*inhal_vape_Y/N*)
[Branching logic exists]

- Yes
 No

If known, please provide the temperature set point of your patient's vaporizer (in °C) _____
(*inhal_vape_temp*)
(125 / 300)
[Branching logic exists]

Calculated, approximated total daily dose of THC and CBD (in mgs)

	THC	CBD
Inhaled	(inhal_THC)  View Equation	(inhal_CBD)  View Equation
Ingested	(ingest_THC)  View Equation	(ingest_CBD)  View Equation

Concomitant medication

Concomitant medication - Existing

Existing NSAIDs and Acetaminophen Dosing Information

At last visit, you indicated that your patient was taking [baseline_visit][nsaid1_name]. Is your patient still taking this medication?

- Yes
 No

What is their current daily dose of [baseline_visit][nsaid1_name] (total mg per day)?

Please select the reason why your patient stopped taking this medication.

- Side effects
 Cost
 Lack of benefit
 No longer needs/ replaced by medical cannabis
 Unknown

At last visit, you indicated that your patient was taking [baseline_visit][nsaid2_name]. Is your patient still taking this medication?

- Yes
 No

Please select the reason why your patient stopped taking this medication.

- Side effects
 Cost
 Lack of benefit
 No longer needs/ replaced by medical cannabis
 Unknown

What is their current daily dose of [baseline_visit][nsaid2_name] (total mg per day)?

At last visit, you indicated that your patient was taking [baseline_visit][nsaid3_name]. Is your patient still taking this medication?

- Yes
 No

Please select the reason why your patient stopped taking this medication.

- Side effects
- Cost
- Lack of benefit
- No longer needs/ replaced by medical cannabis
- Unknown

What is their current daily dose of [baseline_visit] [nsaid3_name] (total mg per day)?

Existing Antidepressants Dosing Information

At last visit, you indicated that your patient was taking [baseline_visit][antidep1_name]. Is your patient still taking this medication?

- Yes
- No

Please select the reason why your patient stopped taking this medication.

- Side effects
- Cost
- Lack of benefit
- No longer needs/ replaced by medical cannabis
- Unknown

What is their current daily dose of [baseline_visit] [antidep1_name] (total mg per day)?

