- No longer needs/ replaced by medical cannabis
- Unknown

What is their current MME?

Existing Other Medications Dosing Information

At last visit, you indicated that your patient was taking other medications, including [baseline_visit][othmed_name]. Is your patient still taking any of these other prescription medications?

- Yes
- No

Please describe any **changes** to their other existing prescription medications since last visit (including changes to total daily dose)

Concomitant Medications - New

Since last visit, has your patient **started** taking any of the following classes of prescription medication (select all that apply)

- Nonsteroidal Anti-inflammatory Drugs (NSAIDs) and Acetaminophen
- Antidepressants (TCA, SNRI, SSRI)
- Anticonvulsants (gabapentin, pregabalin)
- Muscle Relaxants
- Benzodiazepines
- Opioids
- Other
- Medical Cannabis from a Licensed Producer other than Spectrum

Name of new NSAID/Acetaminophen medication (started since last visit)

Daily dose of [physician_1st_follow][nsaid4_name] (total mg per day)

Name of new antidepressant medication (started since last visit)

Daily dose of [physician_1st_follow][antidep4_name] (total mg per day)

Name of new anticonvulsant medication (started since last visit)

Daily dose of [physician_1st_follow][anticon4_name] (total mg per day)

Name of new muscle relaxant medication (started since last visit)

Daily dose of [physician_1st_follow][musrel4_name] (total mg per day)

Name of new benzodiazepine medication (started since last visit)

Daily dose of [physician_1st_follow][benzo4_name] (total mg per day)

Please enter MME (total daily morphine equivalent dose in mg)

Name of new prescription medication (started since last visit, not covered in above classes)

Daily dose of [physician_1st_follow][othmed4_name] (total mg per day)

Physician AE form

Product information

Do you have any adverse events to report related to this patient?

- Yes
- No

Suspect product(s) name

Start date

_____ (YYYY-MM-DD)

End date

_____ (YYYY-MM-DD)

Route of administration

- oral - oil
- oral - softgel
- oral - spray
- oral - beverage
- oral - chocolate
- oral
- inhalation - smoked
- inhalation - vaporized
- inhalation

Dose (please include amount and unit i.e. mg, ml, #softgels, #inhalations, etc.)

Did reaction disappear after reducing the dose or stopping the product ?

- No
- Yes
- Unknown

Did reaction reappear after same product/treatment was restarted?

- No
- Yes
- Unknown

AE description

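### Appendix 4 puts cause and destination in one reason item, so a stop for an adverse event followed by a producer switch may lose its coded cause or draw the wrong eligibility prompt

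*Protocol*

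**What the plan says.** Appendix 4 of the protocol asks the physician "Why did your patient discontinue Spectrum Therapeutics treatment". One of its 13 options is an adverse event. Another is "Patient is obtaining cannabis for medical purposes from a different licensed producer", and two more are also destinations: prescription cannabinoids and a non-licensed source.

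Two messages refer back to this answer. One tells the physician that "they are still eligible for participation in the registry" and asks whether the patient wishes to continue. The other says that "they no longer meet the requirements for participation in the registry" and directs the physician to the Exit Assessment. Neither mentions the separate question "Is your patient obtaining cannabis for medical purposes from an alternative source".

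The form also asks whether the patient still takes medical cannabis, which company supplies it and why the patient changed company. It has a comment field as well. The company-change question reads "Please indicate why (select all that apply)" and has seven options, none of them side effects.

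Section 3.1 bases staying or leaving on the physician's answers to this assessment and gives a switch of licensed producer as an example of withdrawal. Section 6.3 sends subjects who start another licensed producer's cannabis to an Exit assessment, and says that reasons for withdrawal will be kept on record for reporting. Section 2.1.3 makes the tolerability of individual products part of the safety objective.

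**The concern.** Why a patient stopped and where the patient went next are different variables, and both can be true at once. A single list that holds both, and also decides eligibility, makes one answer do two jobs. The two jobs conflict for a patient who stops because of an AE and then takes another licensed producer's product. Section 4.1 makes that case realistic, because subjects in Canada may change producer freely.

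Discontinuation because of an AE is a direct measure of tolerability. If the destination displaces the cause, the coded count can only fall. If the cause displaces the destination, the form may tell the site to keep a subject whom the protocol's own rule withdraws. An analysis plan cannot restore a cause that was never coded, beyond what free text and dates allow.

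**Working it through.** No protocol figure can be reproduced here. The check reads the form against sections 3.1 and 6.3 and traces one case through it.

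**Single or multiple answer?** Six items in Appendices 1 to 4 carry explicit multi-answer wording: three in Appendix 1 and one each in Appendices 2, 3 and 4. The reason item carries none, and the messages speak of the response in the singular. Against this, the seriousness item on the Appendix 2 Physician AE form also lacks such wording, although its options can occur together. Single-answer is therefore the likelier reading, but it is not established.

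**Case traced: the patient stops for an AE, then uses another licensed producer.**

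| Choice | Coded cause | Eligibility prompt |
|---|---|---|
| One answer: AE | Kept | May say still eligible, against sections 3.1 and 6.3 |
| One answer: different producer | Lost from the item | Withdrawal option, in line with sections 3.1 and 6.3 |
| Both, if allowed | Kept | The form does not say which answer governs |

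**Is the cause coded anywhere else?**

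- Company-change list: 7 options, 0 for side effects. By contrast, the Appendix 2 item "Please select the reason why your patient stopped taking this medication" has 5 options, one of which is side effects.
- Appendix 5 (Exit Assessment): a single checkbox.
- Physician AE form: it asks "Did reaction disappear after reducing the dose or stopping the product". This does not separate stopping from a dose cut, and it does not say that the event was why treatment ended.
- Comment field, AE narrative, and AE and product dates: partial recovery only.

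**Is the switch coded anywhere else?** Yes. It can be entered under the alternative-source and company items, if they are displayed, and under the Appendix 2 option for newly started cannabis from another licensed producer.

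**Illustration of size.** The protocol gives no discontinuation or switching rate, so these inputs are assumptions. Per 100 subjects who stop because of an AE, let *s* be the number who move to another producer and *d* the share of those coded to the destination.

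Coded AE count = 100 − *s* × *d*. Possible still-eligible prompts = *s* × (1 − *d*).

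| *d* | *s* = 0: count / prompts | *s* = 20: count / prompts | *s* = 40: count / prompts |
|---|---|---|---|
| 1 | 100 / 0 | 80 / 0 | 60 / 0 |
| 0.5 | 100 / 0 | 90 / 10 | 80 / 20 |
| 0 | 100 / 0 | 100 / 20 | 100 / 40 |

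For example, *s* = 40 and *d* = 0.5 gives 100 − 40 × 0.5 = 80 and 40 × 0.5 = 20. If several answers are accepted, the count stays at 100 when both are ticked.

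**The case against.** The strongest reply is that the premise cannot be seen. Control type and branching are not visible, and the text of a message is not the rule that triggers it. Section 3.1 refers to the physician's answers in the plural, so other items may also drive the decision. This stands, and it is why the point is conditional.

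A reader might go further and infer that such a patient cannot be coded correctly at all. The documents do not support that. The physician can tick the adverse event and record the switch through the alternative-source and company items, or through the concomitant-medication form. Table 1 schedules that form, the Physician AE form and the discontinuation assessment together at an unscheduled visit. The physician can also complete the Exit form whatever the prompt says. What remains is narrower: the reason variable and the routing tied to it. Whether the company item appears after an AE answer is not visible.

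A reader might also infer that the AE itself is lost or the safety endpoint biased. Neither follows. The event has its own form, and the section 7.1 endpoint is AE incidence by product and formulation, not discontinuation because of an AE.

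Finally, section 6.3 promises the reason for withdrawal from the study, and for this subject the producer switch is arguably that reason. This stands in part. It does not supply the reason for stopping treatment, which is what the tolerability objective needs.

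**Conclusion.** The point holds as a minor weakness of form design. It is plain on the page that causes and three destinations share one item, that both eligibility messages cite only that item, and that the company-change list has no side-effect option. The consequence depends on the item being single-answer, which is a reasonable inference and no more. On that condition, one answer cannot give both the AE cause and the option that matches the withdrawal rule. The coded count of AE-related discontinuation may be too low, or a still-eligible prompt may conflict with section 6.3.

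The size is unknown. The illustrative counts of 60 to 100 per 100 AE stoppers rest on assumed shares and say nothing about what will happen in this registry. If several answers are accepted and used, the loss of cause is zero, although the form would still not say which answer governs the prompt.

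**What to change.** In Appendix 4:

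1. State that the reason item accepts several answers, and ask for one primary reason.
2. Add side effects to the reasons for changing company.
3. Show the Exit message whenever a different licensed producer is recorded in any item, whatever the cause.
4. Keep the existing exit routes for death and for no longer wishing to take part. Routing by source alone would leave those two without a path.

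The cost is one eCRF edit with its branching logic. Reasons may then sum to more than 100%, and discontinuations recorded before the change need a flag. If the live form already accepts several answers, step 1 reduces to adding the wording and the primary-reason question.
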